13.4 Primary Objective, Endpoint(s), Analysis Plan

The primary objective of this study is to determine the persistence and stability of serologic geometric mean titer (GMT) of HPV 16/18 between 6, 12, 18, and 24 months after the prime dose and prior to the

administration of the second dose. The primary endpoints are the HPV 16/18 antibody levels at 6, 12, 18, and 24 months. To address the primary objective, the primary endpoint analysis will be evaluating persistence and stability of serologic geometric mean titers (GMT) of HPV16/18 between 6, 12, 18, and 24 months after the prime dose/prior to administration of the second dose. We first propose to perform a one-sided paired t test to compare the difference in the mean of the log-transformed antibody levels between 6 and 12 months, between 12 and 18 months, and between 18 and 24 months respectively, to evaluate whether the GMT at 12/18/24 months, respectively, is not inferior to the GMT at 6/12/18 months. Comparing the difference in the mean of the log-transformed antibody levels is equivalent to comparing the logarithm of the ratio of GMTs since GMT is equal to the exponentiation of log-transformed mean. Bonferroni correction will be used to correct for multiple comparisons (6 vs. 12, 12 vs. 18 and 18 vs. 24).

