The protocol was originally designed to assess the serologic response in girls. Amendment 4 includes the addition of a cohort of boys. Due to limits in the study completion timeline and available study budget, a smaller number of boys than girls will be included in the study to generate pilot data on the serologic response in boys. Boys have been shown to mount a higher serologic response than girls. Therefore, we expect boys and girls to have different responses to the vaccine and will perform the primary analyses for girls and boys separately. For girls, with a sample size of 100 and an overall significance level of 5% (based on Bonferroni correction, i.e. a 1.67% significance level for each test), there will be at least 90% power to detect a non-inferiority margin no greater than 0.35 standard deviations [23]. For boys, with a sample size of 39 and an overall significance level of 5%, there will be at least 80% power to detect a non-inferiority margin no greater than 0.50 standard deviations. In addition, similar to the analysis performed by Safaeian et al. [13], we will also evaluate the stability by categorizing the changes in antibody level from 6 months to 12 months. Specifically, a participant's antibody level at 12 months either remains within two-fold of the level at 6 months (considered as stable) or decreases/increases more than two-fold of the level at 6 months (same for the changes from 12 months to 18 months and from 18 months to 24 months). Percentage of participants whose type-specific antibody levels decrease, increase, or remain stable between the 6 and 12 month study visits, between the 12 and 18 month study visits and between the 18 month and 24 month study visits will be reported along with the associated 95% confidence interval. For girls, a sample size of 100 will produce a two-sided 95% confidence interval with a width ≤ 0.203 based on the exact method approach. For boys, a sample size of 39 will produce a two-sided 95% confidence interval with a width ≤ 0.328 based on the exact method approach.

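### Plain Bonferroni on the three interval tests gives up power that Holm's step-down rule would keep at the same 5% overall error

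*Combined protocol and SAP*

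**What the plan says.** Section 13.4 sets out the primary analysis: "We first propose to perform a one-sided paired t test to compare the difference in the mean of the log-transformed antibody levels", applied to months 6 and 12, 12 and 18, and 18 and 24, separately for girls and boys. On multiplicity it says "Bonferroni correction will be used to correct for multiple comparisons (6 vs. 12, 12 vs. 18 and 18 vs. 24". The power statement for girls fixes the level: "based on Bonferroni correction, i.e. a 1.67% significance level for each test".

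Power is stated for a single test only. For 100 girls, "there will be at least 90% power to detect a non-inferiority margin no greater than 0.35 standard deviations". For 39 boys, at the same overall 5%, "there will be at least 80% power to detect a non-inferiority margin no greater than 0.50 standard deviations".

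No step-down, gatekeeping or other procedure is named for the primary tests. Section 13.5 leaves secondary and exploratory analyses unadjusted. Section 13.1 calls titers persistent and stable when the later visits are non-inferior to the earlier ones, without saying outright that all three intervals must pass.

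**The concern.** Single-step Bonferroni judges each interval against 1.67% whatever the other two show. Holm's procedure gives the same protection against a false claim and can only add successes, so on decisions alone Bonferroni is dominated.

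The loss is largest in the situation the trial expects. The study hypothesis at the end of section 2.3 is stable responses for up to 24 months, in which case all three intervals are truly non-inferior. Under Bonferroni, an interval with p between 1.67% and 5% would be reported as not shown non-inferior even though the other two had passed clearly. Holm would declare it non-inferior whenever those two had p-values at or below 1.67% and 2.5%. The boys have most to gain, because section 13.4 says their number was limited by timeline and budget.

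**Working it through.** **Inputs from the plan (13.4).** Overall level 5%; three tests; one-sided paired t; girls n = 100, margin 0.35 SD; boys n = 39, margin 0.50 SD.

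**Assumptions.** True change is zero, in line with the hypothesis in 2.3. The SD is that of the paired log difference; the text does not say, but the stated power reproduces on this reading. The correlation between interval differences is not given, so a range is used. For adjacent intervals -0.5 (outer pair 0) is what four equally variable, equally correlated visits would produce, because neighbouring differences share a visit with opposite sign. The other cases set all three correlations to 0 or to +0.5.

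**Step 1: the plan's own figures.** Level per test = 0.05/3 = 1.67%. Power = P(T > t at 1 - 0.05/3 with n - 1 df), where T is noncentral t with noncentrality (margin/SD) × √n.
- Girls: 0.35 × √100 = 3.50, power 90.9% (stated: at least 90%).
- Boys: 0.50 × √39 = 3.12, power 81.6% (stated: at least 80%).

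Both reproduce. At the two looser levels that Holm can reach, single-test power is 93.4% (2.5%) and 96.7% (5%) for girls, and 86.1% and 92.2% for boys.

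**Step 2: why Holm is valid and never worse.** Order the p-values and compare them with 5%/3 = 1.67%, 5%/2 = 2.5% and 5%/1 = 5%, stopping at the first failure.
- Never worse: if an interval has p ≤ 1.67%, every smaller p-value is also ≤ 1.67% and so passes its threshold. Holm therefore reaches that interval and passes it.
- Error control: suppose k of the three intervals are truly inferior. The first of these to be wrongly passed faces a threshold no larger than 5%/k. The chance that any of the k p-values is that small is at most k × 5%/k = 5%, whatever the dependence.

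**Step 3: gain when all three intervals are stable.** Simulation, 100,000 trials per row:

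| Group | Correlation | Per interval, Bonferroni → Holm | All three, Bonferroni → Holm | All three, each at 5% |
|---|---|---|---|---|
| Girls | -0.5 | 90.8% → 96.5% | 73.3% → 89.9% | 90.1% |
| Girls | 0 | 90.9% → 96.2% | 75.2% → 90.0% | 90.3% |
| Girls | +0.5 | 91.0% → 95.3% | 80.0% → 91.2% | 91.8% |
| Boys | -0.5 | 81.7% → 91.4% | 49.9% → 76.8% | 77.4% |
| Boys | 0 | 81.6% → 90.5% | 54.4% → 77.5% | 78.6% |
| Boys | +0.5 | 81.6% → 88.8% | 63.5% → 80.9% | 82.5% |

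The difference in the all-three column is the share of trials in which Bonferroni fails at least one interval while Holm passes all three. For correlations of -0.5 and 0 it is 89.9 - 73.3 = 16.6 and 90.0 - 75.2 = 14.8 points for girls, and 76.8 - 49.9 = 26.9 and 77.5 - 54.4 = 23.1 points for boys. The chance of passing at least one interval is identical under both methods.

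**Step 4: overall error.** Simulation, 20,000 trials per setting, over all three correlations and both groups:
- All three intervals at the margin: the two methods are identical, 4.3-5.1%.
- Two at the margin: Bonferroni 3.0-3.5%, Holm 4.4-4.8%.
- One at the margin: Bonferroni 1.4-1.9%, Holm 3.2-4.9%.

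Holm stays at 5% within simulation error. It uses error allowance that Bonferroni leaves unspent.

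**Step 5: gain when stability is only partial.** With one interval at the margin, power for each of the other two rises by about 2 to 3 points (girls) or 3 to 4 points (boys). With two at the margin, the gain in the remaining one is 0 to 0.2 points.

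**The case against.** The strongest reply is that nothing is broken. Bonferroni is valid and prespecified, and the sample size meets its stated power with it. That stands: this is a point about efficiency, not an error.

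Second, the largest gains concern passing all three intervals. If 13.1 means that all three must pass, the test is an intersection-union test and each interval could be tested at 5% with no correction. This is a fair point, and the plan should say which rule applies. It does not rescue Bonferroni: on that reading the correction is more wasteful still, and Holm comes within about 2 points of uncorrected 5% tests (last column of the table). If the intervals are separate claims, the gain per interval is the relevant one, and Holm still wins.

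Third, zero change in every interval is the best case. True, and the gain shrinks as step 5 shows, but it never becomes a loss.

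Fourth, the boys are a pilot cohort, and their 0.50 SD margin appears only in 13.4, while 13.1 gives 0.35 SD alone. At 0.35 SD with n = 39, power per interval is about 50% with Bonferroni and about 59% with Holm. The boys' figures above therefore depend on the 0.50 SD margin, but the direction of the result does not.

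Fifth, every extra Holm success is an interval whose 1.67% confidence limit crosses the margin. Under no change, at least one such visible mismatch would occur in about 15-17% of girls' and 25-28% of boys' analyses. This is the real cost, and someone who wants limits and decisions always to agree could reasonably keep Bonferroni. The plan, however, specifies no simultaneous limits on GMT ratios. Its stated intervals for the primary analysis are 95% intervals for the percentages of participants who are stable, rising or falling, and these are unaffected.

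Last, section 2.3 shows the study had already begun, so this would amend a primary decision rule in an open-label trial. That bears on timing: the change should be dated before the serology is analysed.

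**Conclusion.** The concern holds. Holm gives the same guarantee as the plan's Bonferroni rule from the same p-values and passes everything Bonferroni passes. If titers are stable across all three intervals, and for adjacent correlations of -0.5 to 0, it adds about 5 to 6 points of power per interval for girls and 9 to 10 for boys. For all three intervals together it adds about 15 to 17 points for girls and 23 to 27 for boys. At a correlation of +0.5 the all-three gains are still about 11 and 17 points.

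These sizes rest on zero true change, on margins in SDs of the paired difference, on the stated numbers of evaluable children and on assumed correlations. The dominance itself rests on none of them. The change is worth making; the existing rule is inefficient rather than wrong.

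**What to change.** In 13.4, replace the Bonferroni sentence with wording such as: *The three interval tests for each HPV type will be judged by Holm's step-down procedure at an overall one-sided 5% level, the ordered p-values being compared with 1.67%, 2.5% and 5%.* Adjust the reference to 1.67% per test in the power paragraph to match, and keep the stated 90% and 80% as lower bounds, since Holm can only raise them.

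Applying Holm within each type follows the plan's own division of 5% by three and leaves the handling of HPV 16 and 18 together as it is. Because Holm works on p-values, it also carries over to the signed rank fallback and the multiple imputation in 13.5. If simultaneous limits are wanted, show the 1.67% lower limits beside the Holm decisions and state in advance that the two can disagree and that the Holm result decides. In the same edit, say whether a claim of persistence needs all three intervals.

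The cost is one sentence and its matching cross-reference, made before the serology is analysed. No samples, visits or participants are added.

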(<https://www.cdc.gov/mmwr/volumes/65/wr/mm6549a5.htm>; <https://www.cdc.gov/hpv/hcp/2-dose/clinician-faq.html>). Participants from the youngest of the licensed age groups (9-11 years) are selected for this proof-of-principle study given the potential for younger age children to mount higher immune titers [15], and the fact that immune responses to a single dose or two doses of the HPV vaccines among girls aged 9-14 years appear to be comparable to antibody responses of 3 doses in young women 15-25 years old [9]. The study hypothesis is that a single dose of the nonavalent HPV vaccine will induce persistent and stable serological responses for up to 24 months to all 9 vaccine HPV types in girls and boys 9-11 years of age.

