13. STATISTICAL CONSIDERATIONS

13.1 Study Design/Description

This is a single-arm, open-label, non-randomized, phase IIA trial to determine the immunogenicity of a prime and deferred-booster dosing schedule of a nonavalent prophylactic HPV vaccine (GARDASIL 9) among 9-11 year-old girls and boys. The primary endpoint analysis will be evaluating persistence and stability of serologic geometric mean titers (GMT) of HPV16/18 between 6, 12, 18, and 24 months after the prime dose/prior to administration of the second dose. If the HPV 16/18 antibody level at 12/18/24 months is not inferior to the HPV 16/18/24 antibody level at 6/12/18 months at a non-inferiority margin of 0.35 standard deviation, then the serologic GMT is considered as persistent and stable.

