13.3 Accrual and Feasibility

We plan to accrue 143 eligible girls and 57 eligible boys to receive the deferred-booster schedule of the Gardasil 9. With an anticipated attrition rate of 30%, we expect to have at least 100 girls and 39 boys to complete the 30-month visit. We anticipate to enroll 6-8 participants/per month for each study site and estimate that it will take approximately 12-17 months to complete accrual.

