13.5 Secondary Objectives, Endpoints, Analysis Plans

The secondary objectives include to determine the persistence and stability of serologic GMT of HPV types 6/11/31/33/45/52/58 between 6, 12, 18, and 24 months after prime dose and prior to the administration of the second dose and to assess safety and reactogenicity to each vaccine dose. The secondary endpoints are the antibody levels at 6, 12, 18, and 24 months for each HPV type. Similarly to the primary endpoint analysis, for evaluating persistence and stability of serologic GMT of each HPV type we propose to perform a one-sided paired t test to evaluate the difference in the mean of log-transformed antibody level between 6 and 12 months, between 12 and 18 months and between 18 and 24 months, respectively, to evaluate whether the GMT at 12/18/24 months is not inferior to the GMT at 6/12/18 months. In addition, percentage of participants whose type-specific antibody levels decrease, increase, or remain stable between the 6 and 12 month study visits, between the 12 and 18 month study visits and between the 18 and 24 month study visits will be reported along with the associated 95% confidence interval. A linear mixed effects model with BMI, time and the interaction between BMI and time as the covariates will be performed on antibody level data measured at 6, 12, 18, and 24 months to evaluate whether BMI affects the changes in each specific antibody level.

Similar to the primary analyses, we will perform all of the secondary and exploratory analyses separately for girls and boys. In addition, for all of the secondary and exploratory analyses, adjustment for multiple comparisons will not be performed. However, the number of comparisons will be reported and we will also cautiously interpret the findings. For both primary and secondary endpoints, if the normality assumption is violated, potential transformation will be sought or nonparametric methods such as signed rank test will be performed.

We will try to reduce the fraction of participants with missing outcomes as much as possible. The covariates (e.g. BMI, BSA, and sociodemographics) that are predictive of missing-ness for each outcome at each visit (i.e. 6, 12, 18 and 24 months) will be identified through use of logistic regression for each missing indicator and then incorporated into multiple imputation procedures to handle missing data while performing the statistical analysis for both primary and secondary endpoints.

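### Section 13.1 draws one conclusion from three intervals without saying whether all must pass; the power in 13.4 is for a single test, and the boys' margin differs between the two sections

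*Combined protocol and SAP*

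**What the plan says.** Section 13.1 gives the decision rule in one conditional sentence. Levels at 12/18/24 months are compared with levels at 6/12/18 months, and if they are not inferior "at a non-inferiority margin of 0.35 standard deviation, then the serologic GMT is considered as persistent and stable". The sentence contains neither an all nor an each, and it makes no exception for boys.

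Section 2.3 states the hypothesis that one dose "will induce persistent and stable serological responses for up to 24 months to all 9 vaccine HPV types".

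Section 13.4 runs one-sided paired t tests on log titres "between 6 and 12 months, between 12 and 18 months, and between 18 and 24 months respectively", and adds: "Bonferroni correction will be used to correct for multiple comparisons (6 vs. 12, 12 vs. 18 and 18 vs. 24"). For 100 girls at 0.35 SD the power statement reads "based on Bonferroni correction, i.e. a 1.67% significance level for each test), there will be at least 90% power". For 39 boys it is "at least 80% power to detect a non-inferiority margin no greater than 0.50 standard deviations". Girls and boys are analysed separately. No power is given for passing all three intervals.

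Section 13.3 says where the sample sizes come from: "we expect to have at least 100 girls and 39 boys to complete the 30-month visit".

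**The concern.** The two sections point to different rules. One verdict covering three intervals, together with a hypothesis of stability up to 24 months, reads most naturally as a claim that fails if any interval fails. Under that rule (an intersection-union test) each interval can be tested at the full 5% without inflating the error of the overall claim, and the relevant power is the chance that all three pass. A Bonferroni family of three with power per test instead suits three separate claims.

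If 13.1 needs all three, following 13.4 tests the conclusion at no more than 1.67% rather than 5%, and the conclusion lacks the power quoted. If two intervals pass and one fails, the plan does not say what may be concluded, and the choice could be made after the results are known.

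The boys' margin is a further conflict that does not depend on how the intervals combine.

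**Working it through.** **Inputs.** From 13.4: one-sided paired t test; overall level 5%, so 0.05/3 = 1.67% per test; girls n = 100, margin 0.35 SD; boys n = 39, margin 0.50 SD. From 13.1: margin 0.35 SD. From 13.3: 143 girls enrolled, 30% attrition by month 30.

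**Assumptions not in the documents.** The true change is zero. The SD is that of the paired log difference. The correlation between interval changes is not given, so -0.5 to +0.8 is shown; zero or negative values are what serial titres usually produce (a constant personal level plus independent error gives -0.5 for adjacent changes).

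**Step 1: the plan's own figures.** Power of one test = P(T > t(1-α; n-1)), where T is noncentral t with n-1 degrees of freedom and noncentrality margin × √n.
- Girls: 0.35 × √100 = 3.5; at 1.67% the power is 90.9%. The stated 90% is reproduced.
- Boys: 0.50 × √39 = 3.12; at 1.67% the power is 81.6%. The stated 80% is reproduced.

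**Step 2: all three intervals, per HPV type.** With independent changes, joint power is the cube of single-test power: 0.9085³ = 0.750 at 1.67% and 0.9665³ = 0.903 at 5%. Whatever the correlation, it cannot fall below 1 - 3 × (1 - power): 72.6% and 89.9%. Other correlations were simulated. The linear-attrition row assumes n = 143 × (1 - 0.3 × month/30), rounded down, which gives 125, 117 and 108 at months 12, 18 and 24.

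| Girls, 0.35 SD | 1.67% per test | 5% per test |
|---|---|---|
| Single test, n = 100 | 90.9% | 96.7% |
| All three, n = 100, correlation -0.5 to 0 | 73-75% | about 90% |
| All three, n = 100, correlation +0.3 to +0.8 | 78-84% | 91-94% |
| All three, linear attrition, correlation -0.5 to +0.8 | 84-89% | 95-96% |

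**Step 3: both HPV types required.** If all six tests were independent: 0.9665⁶ = 0.815 at 5% and 0.9085⁶ = 0.562 at 1.67%.

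**Step 4: error rates, girls, n = 100.** Under the all-three rule, with one interval at the margin and the others clear of it, the simulated type I error is 4.9-5.1% at 5% per test and 1.6-1.7% at 1.67%. Under separate claims with all three changes at the margin, the chance of at least one false interval claim is 9-15% at 5% per test and 3-5% at 1.67%.

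**Step 5: boys, n = 39.** At the 0.35 SD of 13.1 the noncentrality is 0.35 × √39 = 2.19.

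| Boys | 1.67% per test | 5% per test |
|---|---|---|
| 0.50 SD, single test | 81.6% | 92.2% |
| 0.50 SD, all three, correlation -0.5 to 0 | 50-54% | 77-78% |
| 0.35 SD, single test | 49.7% | 69.2% |
| 0.35 SD, all three, correlation -0.5 to 0 | 5-13% | 25-33% |

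**The case against.** The strongest reply is that 13.4 is the operative text and describes separate tests. It pairs the intervals respectively, lists them as the Bonferroni family, and gives the per-test level in the same sentence as the power. On that reading, with HPV16 and HPV18 as separate families, the divisor of three and both stated powers are correct. This stands, so the all-three reading is well supported by 13.1 and 2.3 but not stated.

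A reader might infer that the 90% was miscalculated, that the split is an error in itself, or that girls' power simply falls short of 90%. The documents support none of these. The 90% is right per test. The shortfall needs both the all-three rule and the split kept. The top figure of 89% also needs an assumed attrition pattern and a correlation of +0.8. Nor is there a risk of more false claims: the current text is, if anything, conservative.

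Three limits on the all-three reading also stand. First, the slash notation that suggests all intervals could equally mean both HPV types, so a per-type rule has to be written down. Section 13.5 speaks of "evaluating persistence and stability of serologic GMT of each HPV type", but only for the secondary types. Second, only consecutive visits are compared, so even an all-three rule does not test month 24 against month 6. Third, 100 is the number expected at month 30, after the last primary comparison, and 13.5 plans multiple imputation, whose effect on power cannot be worked out from the documents.

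Finally, this is a Phase IIA proof-of-principle study and the boys are described as pilot data. That limits the consequence but does not resolve the conflicting margins.

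**Conclusion.** The point holds conditionally for the decision rule and unconditionally for the boys' margin.

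If all three intervals are required, the plan as written has about 73-75% power per type for girls, where 13.4 shows 90%. A stable response would be missed about one time in four, or about one in six under linear attrition with zero or negative correlation. Dropping the split brings joint power to about 90% or more. If separate interval claims are intended, the figures in 13.4 are right and the single conclusion in 13.1 is what does not fit.

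The figures assume no true decline and leave little reserve. With a true fall of 0.05 SD per interval and independent changes, joint power at n = 100 is about 75% at 5% per test and 51% at 1.67%.

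For boys, 13.1 and 13.4 cannot both govern. At 0.35 SD the single-test power is about 50%, not 80%. The loss throughout is power and a clear decision rule, which should be put right because wording and restated figures are enough.

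**What to change.** Before serology results are seen, write one rule in both 13.1 and 13.4.

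1. **Single conclusion.** For each HPV type, conclude persistence and stability only if all three interval comparisons show non-inferiority, each at one-sided 5%, with no split over intervals. Report joint power (girls about 90% per type at n = 100, 0.35 SD, no true decline) and label the present 90% and 80% as per-test figures at 1.67%.
2. **Separate conclusions.** Keep the split and the 90%/80%, labelled as per-test figures, and replace the single conclusion in 13.1 with one per interval.

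Under either option, state how HPV16 and HPV18 combine: as separate 5% families, or both required. If both are required under option 1, girls' power is about 81% when the six tests are independent. Reconcile the boys' 0.35 and 0.50 SD margins, and restate their power for the margin kept.

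The cost is wording and restated power, with no new participants or data. Option 1 tests each interval at a looser level, so the split may be dropped only if the all-three rule is written in. Without that rule, the chance of at least one false interval claim per type rises to 9-15% in the setting of step 4. Option 2 changes no numbers but gives up the single 24-month conclusion.
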